10.5 Protocol Deviations and Violations

10.5.1 Investigators acknowledge that they are not permitted to deviate from this Protocol, except in emergency circumstances.

Under emergency circumstances, deviations from the protocol to protect the rights, safety and well-being of human subjects may proceed without prior approval of the Sponsor or reviewing IRB/REB. Such deviations will be recorded and reported to the Sponsor and reviewing IRB/REB as soon as possible.

All protocol deviations and violations shall include a corrective and preventive action plan to assist in the limiting of deviations from the Protocol in the future.

10.5.2 All protocol deviations (i.e. any change, divergence or departure from the procedures or protocol) shall be recorded with an explanation for the deviation on the Protocol Deviation Form. A simple protocol deviation does not impact the subjects' rights, safety, or well-being, or the completeness, accuracy or reliability of the study data. Deviations shall be reported by the Investigator to Zimmer Biomet within 30 days. Zimmer Biomet will analyze the information and assess the significance. Deviations must also be reported to the reviewing IRB/REB per policy.

Any deviations to inclusion or exclusion criteria must be submitted to Zimmer Biomet in writing, per section 10.5.4 and the reviewing IRB/REB, where applicable, for analysis and approval prior to subject enrollment.

10.5.3 All protocol violations (i.e. any deviation from the protocol that may impact the subjects' rights, safety, or well-being, or the completeness, accuracy or reliability of the study data, or a deviation from FDA or IRB/REB regulations or standards) shall be reported to Zimmer Biomet within 24 hours and to the reviewing IRB/REB per policy. A Protocol Deviation Form shall be completed that includes a full explanation of the event and outcome.

The Investigator will assist Zimmer Biomet in corresponding with the reviewing IRB/REB, where appropriate, to determine the appropriate course of action.

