10.5.4 Protocol waivers/exceptions may be granted by the Sponsor on a case by

case basis as per request from sites. A description and rationale for the exception request should be put in writing on a Protocol Waiver/Exception Request Form. A Site Investigator will be required to sign off on the form, as well as a Sponsor Approver, prior to the enrollment of a subject or known deviation from the protocol. Should a deviation or violation be performed without prior written approval from all parties, the Investigator may be terminated from the study. Any deviation or violation from the protocol should be captured on a Protocol Deviation Form.

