14.8 Analyses Populations

Subjects will be assigned a subject ID number after verification that they met the preliminary study criteria, have signed the informed consent form, scheduled a surgery date and Inclusion/Exclusion has been entered into the Electronic Data Capture System. A Randomization ID will be assigned just prior to the time of surgery.

The **intent-to-treat (ITT)** population is defined as subjects who complete the preoperative procedures and are randomized just prior to the time of surgery. The final determinations of inclusion and exclusion criteria and stratum assignment are made during surgery. The allowable exclusions will be any subject who does not meet inclusion or exclusion criteria based on surgeon review. Preoperative and surgical data will be collected from these subjects, along with the reason for the subject being excluded from the study. However, the subject will be exited and will not continue for follow-up. The baseline analyses and analyses of population characteristics will be performed on the ITT group.

The **modified ITT (mITT)** population is defined as subjects who meet all inclusion and exclusion criteria and have an arthroscopy with SCP or arthroscopy alone as outlined in Section 9.5. The modified ITT population will be used for the primary and secondary efficacy analyses and safety analyses.

The **per-protocol (PP)** population is all subjects who are assigned a study number, receive treatment as randomized per the study procedure and complete the study according to the protocol. Exclusions for the per-protocol analysis population include, but are not limited to, protocol violations and any actions that compromise the efficacy of the procedure. The primary variables analyses will be done on this population to determine if study findings would have differed with the inclusion of the excluded subjects.

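### Read literally, the mITT definition leaves subjects operated on under an approved eligibility waiver out of the primary test and the adverse event rates by arm

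*Combined protocol and SAP*

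**What the plan says.** Two parts of the combined protocol and SAP bear on this.

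**Waivers.** Section 10.5.2 requires that "Any deviations to inclusion or exclusion criteria must be submitted to Zimmer Biomet in writing, per section 10.5.4", and, where applicable, to the ethics board, for approval before the subject is enrolled. Section 10.5.4 lets the sponsor grant exceptions one case at a time. The site investigator and a sponsor approver must sign "prior to the enrollment of a subject or known deviation from the protocol". It also says: "Any deviation or violation from the protocol should be captured on a Protocol Deviation Form".

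**Analysis sets.** Section 14.8 defines ITT as "subjects who complete the preoperative procedures and are randomized just prior to the time of surgery" and assigns it the baseline and population-characteristics analyses. It defines mITT as "subjects who meet all inclusion and exclusion criteria and have an arthroscopy with SCP or arthroscopy alone as outlined in Section 9.5" and states: "The modified ITT population will be used for the primary and secondary efficacy analyses and safety analyses". PP consists of subjects who have a study number, were treated as randomised and completed the study according to the protocol. Protocol violations are among its exclusions, and it is used to repeat the primary analysis. None of the three definitions mentions waivers.

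**The concern.** The waiver route is a planned way into the trial for subjects who fail a criterion. The mITT definition is a stated rule that keeps such subjects out of the main analyses. If both are followed as written, a subject can be admitted with the sponsor's agreement, randomised and operated on, then left out of the comparison.

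Two things are at stake:

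- **Safety reporting.** Section 5.7.4 names the entry criteria as a means of limiting risk. Subjects admitted outside them are those whose adverse events a reader would most want counted, yet the rates by arm would omit them.
- **A fixed primary population.** If waived subjects exist, the analyst must either apply the definition and drop them after randomisation, or keep them and depart from the definition. The synopsis and section 7.0 report an interim analysis in which success in the control arm was higher than expected. Outcome information on at least that arm is therefore already known, and the choice should not be left open until the final analysis.

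**Working it through.** The plan gives no figure on this point: it states neither a number of waivers nor the size of any set after removing them. The check is therefore a comparison of passages.

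1. **Does the waiver route cover eligibility?** Yes. Section 10.5.2 sends departures from the inclusion and exclusion criteria to section 10.5.4, with approval before enrolment.

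2. **Does approval turn a failed criterion into a met one?** No section says so. Section 10.5.4 has every deviation entered on the deviation form and makes no exception for approved ones, so the subject still counts as deviating.

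3. **Where does such a subject fall?**

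| Set | Deciding condition | Subject operated on under a waiver | Named use |
|---|---|---|---|
| ITT | Preoperative procedures done, randomised | In | Baseline and population characteristics |
| mITT | Every entry criterion satisfied, and operated on | Out, read literally | Primary, secondary and safety analyses |
| PP | Study number, treated as randomised, completed per protocol; violations excluded | Not determined | Primary variables (14.8); secondary endpoints (implied by 10.4.3); not safety |

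4. **Why PP is undetermined.** Section 10.5 separates deviations (10.5.2) from violations (10.5.3) and deals with eligibility departures under deviations. PP excludes violations, but its list is expressly open-ended. Section 14.4 also ties the study number to having met study criteria. If PP does admit waived subjects, it contains subjects whom mITT excludes, so it is no longer a subset of mITT.

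5. **Does the missing-data plan bring them back?** No. Section 14.9 runs the primary test on mITT. The tipping-point analysis and the multiple imputation cover mITT subjects who lack an outcome, not subjects outside mITT.

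6. **Effect on a reported safety rate.** Suppose that in one arm n subjects were operated on and e had a given event, and that w of the n were waived, e_w of them with the event. The rate in all operated subjects is e/n. The mITT rate is (e − e_w)/(n − w). The two coincide if w = 0; otherwise the waived subjects leave both numerator and denominator. The documents give no value for w.

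7. **Is the route more than theoretical?** The document history places the waiver section in version 4.0, dated 23 July 2019, and the synopsis says recruitment ran from May 2017 to November 2020 (42 months). The written route was therefore in the protocol for about the last 16 of those months (July 2019 to November 2020). Whether it was used for eligibility is not stated.

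**The case against.** The strongest reply is that this is a gap in wording that may concern nobody. No waiver is reported. Section 9.1 counts as enrolled only subjects who meet the pre-surgery criteria, and section 9.4 has randomisation follow confirmation of all criteria. A sponsor could therefore treat a waived criterion as met, which would put the subject in mITT already. That intention is possible, but it is not written, and the deviation-form rule in 10.5.4 points the other way.

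Several stronger readings are tempting, and the documents do not support them:

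- **That waived subjects are analysed nowhere.** They are in the ITT baseline summaries and may qualify for PP, on which the primary variables are repeated. Sections 10.4.3 and 10.4.6 also mention two-year follow-up for an ITT analysis, although section 14 defines no ITT outcome analysis.
- **That their follow-up is complete.** No section describes follow-up of waived subjects. The exit rule in 14.8, for subjects found not to meet the criteria on surgeon review, makes no exception for them.
- **That their safety data are lost.** Sections 11.0 and 12.0 have reportable events recorded, entered in the database and reviewed by the sponsor, and 14.7 promises listings of all events. What the mITT rule removes is their contribution to the rates by arm.
- **That 10.5.1 contradicts 10.5.4.** Section 10.5.1 says "Investigators acknowledge that they are not permitted to deviate from this Protocol, except in emergency circumstances". Section 10.5.4 concerns exceptions signed in advance and penalises those made without approval. Together they can be read as barring only unapproved deviations.
- **That power suffers.** Any figure would need an assumed number of waivers and the planned total of 201, although enrolment was stopped early.

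**Conclusion.** The point holds in limited form. Under the text of section 14.8, a subject enrolled under a section 10.5.4 eligibility waiver and operated on is outside mITT. That subject is therefore missing from the primary test and from the adverse event rates by arm, and is certain to appear only in the ITT baseline summaries.

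This rests on reading the mITT definition literally, and on an approved waiver not counting as meeting the criterion; the documents do not say that it does. The size is unknown and may be zero, and no loss of power or bias of stated size is claimed. The safety part matters most, because PP, the one outcome set that might still hold these subjects, is not named for safety. The change is worth making because it costs almost nothing and settles the primary population in writing before the final analysis.

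**What to change.** Amend section 14.8 as follows:

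1. Base the safety analyses on every subject in whom the study operation was started, not on mITT. This also counts events up to exit in subjects found ineligible during surgery.
2. State that subjects with an approved 10.5.4 eligibility waiver belong to mITT in their randomised arm.
3. State whether those subjects belong to PP.
4. Add one sensitivity analysis that repeats the primary test without them.

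The final report should give the number of eligibility waivers by arm; if there were none, it should say so, and item 4 falls away.

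The cost is a few sentences of SAP wording and one extra run, with no new data collection. The downside is that a few protocol-ineligible subjects stay in the primary set; the sensitivity analysis shows whether they affect the conclusion.

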9.5.2 Subchondroplasty Procedure

After randomization to the study group, subjects assigned to the SCP + Arthroscopy group will undergo the Subchondroplasty portion of the procedure before or after the Arthroscopy portion per the surgeon's discretion. All operative procedures are to be performed under aseptic conditions according to the institution's standards. The same Arthroscopic procedures reported above for Arthroscopy Control subjects should be performed for Subchondroplasty + Arthroscopy subjects. The Subchondroplasty surgical technique is described in detail in Appendix B, with the required steps outlined below.

- The preoperative MRI should be used in planning the access point, trajectory and depth of the AccuPort® cannula(s) for accessing the location of the BML(s).
- AccuPorts should be placed using fluoroscopic guidance.
- Use of the SCP Navigation guide is optional.
- AccuFill should only be mixed with saline, for consistency between subjects.
- Appropriate volume of AccuFill should be used to adequately fill the area(s) of BML(s) taking care not to over-pressurize or overfill the defect. Multiple fluoroscopic images should be taken during injection to check for extravasation of material.
- Any extravasation of material into surrounding soft tissues should be

thoroughly irrigated at the time of the procedure.

- An arthroscopic examination of the joint should be performed after injection to check for any material in the joint space. Any material found should be evacuated from the joint utilizing suction and lavage.

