14.2 Hypotheses

The primary hypotheses to be tested are symbolically represented as:

$$H_0: CCS(S+A) \leq CCS(AA) \text{ VS } H_a: CCS(S+A) > CCS(AA)$$

Where CCS(S+A) and CCS(AA) are equal to the probabilities of achieving composite clinical success for subjects undergoing Subchondroplasty with arthroscopy (S+A) compared to arthroscopy alone (AA). First, superiority will be statistically tested at 12 months using $\alpha=0.01$. If $p \leq 0.01$, then it will be concluded that S+A is superior to AA in terms of the primary endpoint and the conditional hypothesis of superiority in terms of ADL improvements will be tested, also at $\alpha=0.01$. If $p > 0.01$ at month 12, the same

hypothesis will be tested at month 24 using $\alpha=0.04$, thereby controlling the overall study type 1 error rate to no more than 0.05 according to the Bonferroni inequality. If $p \leq 0.04$ at month 24, it will be concluded that S+A is superior to AA in terms of the primary endpoint and the conditional hypothesis of superiority in terms of ADL improvements will then be tested at $\alpha=0.04$. The superiority hypotheses involving CCS will be tested using one-sided normal approximation tests. The conditional superiority test for improvements in ADL will be tested using one-sided contrasts derived from a mixed model for repeated measures (MMRM) for change in KOOS ADL among subjects free from SSSI.

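### Membership of the primary efficacy and safety set (mITT) depends on a Section 9.5 procedure having been performed, and the plan does not say that mITT subjects are analysed as randomised

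*Combined protocol and SAP*

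**What the plan says.** Section 14.8 defines three sets.

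- **ITT** is the set defined by randomisation, but its use is limited: "The baseline analyses and analyses of population characteristics will be performed on the ITT group".
- **mITT** requires that subjects meet all eligibility criteria and "have an arthroscopy with SCP or arthroscopy alone as outlined in Section 9.5". Its role is wide: "The modified ITT population will be used for the primary and secondary efficacy analyses and safety analyses".
- **Per-protocol** requires that subjects "receive treatment as randomized per the study procedure and complete the study according to the protocol". This is the only one of the three definitions that refers to treatment as randomised.

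Section 9.5 describes the two operations. Section 9.5.1 lists the permitted arthroscopic procedures, sets limits on them, and adds superficial skin incisions for controls. Section 9.5.2 calls for the same arthroscopic procedures in S+A and adds the injection, "with the required steps outlined below". Those steps include fluoroscopic placement, mixing with saline only, adequate fill, and an arthroscopic check after injection.

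Section 14.9 confines the tipping-point and multiple-imputation analyses to mITT subjects.

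**The concern.** A primary set that depends on how the operation went is selected after randomisation. An S+A subject whose injection was abandoned, or in whom a required step was missed, did not have the S+A procedure as Section 9.5 sets it out. On the literal wording that subject is not in mITT. Such cases may be failures of the treatment under test, and removing them may flatter it.

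No planned analysis would bring them back. The missing-data analyses start from mITT, the per-protocol set is narrower still, and no CCS analysis of all randomised subjects is planned. Because mITT is also the safety set, the adverse event rates could lose the same subjects.

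The plan also does not name the arm in which an mITT subject is counted. Two analysts could form different primary sets from the same data, and the choice could be made after outcomes are known.

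**Working it through.** **1. The plan's own figure.** Inputs from Sections 14.2 and 14.5: CCS 0.60 for arthroscopy alone (AA) and 0.80 for S+A, allocation ratio r = 2, one-sided alpha 0.04 (the month 24 level), power 80%. With z = 1.751 and 0.842, and weighted mean rate (0.60 + 2 × 0.80)/3 = 0.733:

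- n(AA) = [1.751 × √(3 × 0.733 × 0.267) + 0.842 × √(2 × 0.24 + 0.16)]² / (2 × 0.20²) = 50.7
- with continuity correction: (50.7/4) × [1 + √(1 + 6/(50.7 × 2 × 0.20))]² = 57.97, so 58 AA and 116 S+A, total 174.

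This matches the plan. 174 × 1.15 = 200.1, which the plan takes to 201. An as-randomised rule changes neither number.

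**2. Who can fall outside Section 9.5.**

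| Condition | S+A | AA |
|---|---|---|
| No cartilage repair beyond debridement, no treatment of osteophytes next to the target lesion, no root repair | yes | yes |
| Skin incision at the usual access points, closed in the typical fashion | not separate | yes |
| Required injection steps of 9.5.2 | yes | no |

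Both arms can fail. S+A has more ways to do so.

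**3. Effect of dropping non-conforming S+A subjects.** The documents give no rate of non-conformance and no outcome for these subjects, so f and q below are assumptions. Let p be the true CCS in both arms as randomised (no treatment effect), f the non-conforming fraction of S+A, and q their CCS.

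- CCS among those kept: c = (p − f·q)/(1 − f)
- Spurious difference: c − p
- SE = √[c(1 − c)/(116(1 − f)) + p(1 − p)/58]
- Type I error = 1 − Φ(1.751 − (c − p)/SE)

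Example with p = 0.80, f = 0.05, q = 0.50:

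- c = (0.80 − 0.025)/0.95 = 0.8158, a difference of 0.0158
- SE = √(0.8158 × 0.1842/110.2 + 0.16/58) = 0.0642, ratio 0.246
- error = 1 − Φ(1.505) = 0.066.

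| p | f | q | Spurious difference (points) | Type I error (nominal 0.04) |
|---|---|---|---|---|
| 0.80 | 5% | 0.80 | 0 | 0.040 |
| 0.80 | 5% | 0.70 | +0.5 | 0.048 |
| 0.80 | 5% | 0.50 | +1.6 | 0.066 |
| 0.80 | 10% | 0.50 | +3.3 | 0.11 |
| 0.60 | 5% | 0.40 | +1.1 | 0.053 |

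Enrolment stopped early, so 116 and 58 may not be reached. At half that size (58 and 29), the 0.066 becomes about 0.057.

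**The case against.** The strongest reply is that these subjects would be kept and analysed in S+A. The set is called modified ITT. Sections 9.5.1 and 9.5.2 describe each operation for subjects assigned to that group. The per-protocol set has its own as-randomised condition and excludes protocol violations, much of which would be redundant if mITT already demanded step-level conformity. Sections 10.4.3 and 10.4.6 keep revised and unblinded subjects in follow-up for ITT analysis. Section 10.5 handles departures by deviation form, and no section says that a deviation removes anyone from mITT. This makes retention a possible reading, so exclusion cannot be stated as certain. It does not remove the condition in the definition or supply the missing rule on arm.

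Other parts of the reply also stand:

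- The bias depends on the assumed outcome. A subject whose injection was aborted still had an arthroscopy; if prognosis is average, the bias is zero.
- Extravasation alone is not a departure, because Section 9.5.2 provides for it.
- Safety events are still recorded, and the listings in Section 14.7 cover all events. The rate tables are what is exposed.

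Three stronger readings are tempting but not supported:

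- **That non-conforming S+A subjects are counted as arthroscopy alone.** Section 14.2 does frame the hypothesis by the procedure undergone. But Section 9.5.1 describes arthroscopy alone for subjects assigned to control, and a subject who received material did not have arthroscopy alone. The larger errors this would give (about 0.14 at 5% and 0.33 at 10%, with p = 0.80 and q = 0.50) are therefore not relied on.
- **That the condition acts on S+A only.** The table in step 2 of the working shows that controls can fail it too.
- **That subjects treated before the saline-only step was added in version 2.0 fall outside the set.** The document history describes superseded text. Nothing says earlier subjects were treated differently or would be judged against a later version.

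**Conclusion.** The point holds as a gap in the definition of the primary and safety set. Section 14.8 ties mITT membership to the operation performed after randomisation and does not state an as-randomised rule. Exclusion of non-conforming subjects is the most literal reading, not a certain consequence.

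If non-conforming S+A subjects are dropped and do worse than average, the comparison tilts towards S+A. With CCS 0.80 in both arms, 116 and 58 evaluable and one-sided alpha 0.04, the error is about 0.048 to 0.066 at 5% non-conforming, and about 0.11 at 10% with their CCS at 0.50. These figures show scale only: the non-conformance rate and the outcome of these subjects are assumed, and the bias is zero if their outcome is average.

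**What to change.** In Section 14.8:

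1. Remove the reference to Section 9.5 from the mITT definition.
2. Define the efficacy set as all randomised subjects whose index arthroscopy was started and who were not exited as ineligible at surgery under the existing rule. Analyse each in the randomised arm, whatever procedure was then performed. The carve-out is needed because subjects found ineligible at surgery leave without follow-up and have no CCS.
3. Keep conformity with Section 9.5 as a per-protocol criterion only.
4. Define a separate safety set of every subject operated on, tabulated by procedure received, with aborted or non-conforming injections shown separately.

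The tipping-point and imputation analyses of Section 14.9 would then cover the wider set. The cost is a change of wording before the data lock in Section 17.3. It needs no new data, and the sample size stays at 174 and 201. The S+A success rate may look slightly less favourable.

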7.0 Study Design

This is a multicenter, prospective, single-blinded, two-arm, randomized study. Enrolled subjects will have a single BML of the tibia, single BML of the femur, or adjoining BMLs of tibia and femur, as long as the BMLs are in the same compartment of the knee. Subjects will also be surgical candidates for knee arthroscopy due to mechanical symptoms, meniscus tear, loose body and/or synovitis.

A stratified blocked randomization will be used to assign subjects to either Subchondroplasty with arthroscopy or to arthroscopy alone in a 2:1 ratio. Individual sets of blocks will be determined within study site and lesion polarity status (unipolar vs bipolar).

Subjects will be consented within 90 days prior to surgery and take part in follow-up visits for two years following surgery. A preoperative visit (with exception of MR imaging) will occur within 60 days prior to surgery. Telephone follow-up interviews will be done at 6 weeks, 3 months, 6 months, 9 months, 18 months and 24 months post-surgery. Target enrollment is 201 subjects, to include 134 subjects in the treatment group (SCP + Arthroscopy) and 67 subjects in the control group (Arthroscopy alone).

Enrollment was stopped early when an interim analysis demonstrated that the study was unlikely to meet its primary endpoint due to an unexpectedly high success rate in the arthroscopy only group. Follow-up will continue for all subjects enrolled through the 24 month visit to allow further monitoring of outcomes related to revisions, reoperations, adverse events, and to collect KOOS assessments and numeric pain scores.

Subjects will complete the study at the 24 month follow-up visit. For the purposes of this protocol, a revision will be defined as any partial or total joint arthroplasty or any bone fixation, bone grafting or bone substitute procedure in the same compartment in the study knee.

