10.4.2 Surgical Reoperation or Revision

A reoperation of the index knee or revision of the SCP injection site may be performed at the discretion of the Investigator (e.g., due to progressive pain or disability, clinical or radiographic evidence of potential graft failure, etc.). A reoperation is defined as any surgical procedure on the index knee. For the

purposes of this protocol, a revision will be defined as any partial or total joint arthroplasty or any bone fixation, bone grafting or bone substitute procedure in the same compartment in the study knee.

The investigator is to dictate detailed operative notes that include the measures listed below, or have paper copies of the Surgical Reoperation Form completed during surgery to serve as a source document.

10.4.3 *Surgical Reoperation Documentation*

- Reason for Surgery
- Postoperative Diagnosis
- OR Time
- Anesthesia Type

All reoperations should be documented on an Adverse Event Form and the surgery documented on the Surgical Reoperation Form.

In the event that a revision occurs (defined as any partial or total joint arthroplasty or any bone fixation, bone grafting or bone substitute procedure in the same compartment in the index knee), the subject will be excluded from any future per protocol (PP) analysis of secondary endpoints, but should continue to be followed through the two-year endpoint for ITT analysis. An Adverse Event Form and Surgical Reoperation Form will be completed.

In the event that a reoperation occurs that does not involve revision of the BML site(s), an Adverse Event Form and Surgical Reoperation Form will be completed, and the subject will continue to be followed in the study per protocol. If possible, reoperations should not be performed within 6 weeks of the 12 and 24 month visits.

10.4.4 *Subject Cross-over Between Treatment Groups*

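### The per-protocol run of the primary endpoint requires completion to month 24, so a known CCS failure who leaves early drops out of it, and no set is defined for the month-12 test

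*Combined protocol and SAP*

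**What the plan says.** Section 14.8 assigns the confirmatory work to the modified ITT set: "The modified ITT population will be used for the primary and secondary efficacy analyses and safety analyses". It then defines a PP set of subjects who "receive treatment as randomized per the study procedure and complete the study according to the protocol". Exclusions from that set are an open-ended list that covers "protocol violations and any actions that compromise the efficacy of the procedure". The set has a stated job: "The primary variables analyses will be done on this population to determine if study findings would have differed".

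Section 7.0 fixes the point of completion: "Subjects will complete the study at the 24 month follow-up visit". Section 14.2 tests CCS at month 12 and, if that test fails, again at month 24. Section 14.8 gives one PP definition for both.

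Section 10.4.3 (Surgical Reoperation Documentation) says that after a revision "the subject will be excluded from any future per protocol (PP) analysis of secondary endpoints", but that the subject "should continue to be followed through the two-year endpoint for ITT analysis".

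**The concern.** CCS counts a subsequent arthroplasty or bone procedure on the study knee (SSSI) as a failure. Once it has happened, no later visit can change that status. A PP rule that also asks for completion at month 24 can discard such a subject although the primary outcome is already known. At month 12 the rule goes further, because who counts depends on follow-up that comes after the outcome being tested.

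The PP run is there to show whether the result depends on who is left out. If membership depends partly on the outcome, agreement between PP and mITT reassures less than it appears to, and disagreement is hard to interpret.

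**Working it through.** **The plan's own figure.** Section 14.5 assumes CCS rates of 0.80 (S+A) and 0.60 (AA) and needs 116 + 58 = 174 subjects for 80% power. A one-sided normal test at 0.04 with 2:1 allocation and continuity correction gives 58 in AA, so 174 in total; without the correction it gives 51, so 153. Then 174 × 1.15 = 200.1, taken up to 201 (134:67). The figure reproduces and does not depend on the PP definition. It supplies the rates used below.

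**Who the completion rule removes.**

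- *SSSI at month 5, exit at month 8.* CCS failure at both tests. Section 10.6 keeps data collected before withdrawal in the database unless the subject asks otherwise in writing, so the failure is normally on record. The subject did not complete the study and is not in the PP set.
- *Observed KOOS pain failure at month 12, exit at month 15.* Known failure for the month-12 test, not in the PP set.
- *KOOS pain success at month 12, exit at month 15.* Known success for the month-12 test, also not in the PP set.
- *SSSI or KOOS pain failure, followed to month 24.* Meets the completion rule and stays in as a failure unless excluded on other grounds.

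At month 24 a leaver without an SSSI has no CCS status, so the subjects with known status whom the rule removes are failures. At month 12 it can remove both failures and successes.

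**Sections 14.8 and 10.4.3 side by side.** The definition of revision in 10.4.3 matches the SSSI definition in 14.1. Section 10.4.3 limits the PP exclusion to secondary endpoints, which implies that a revised subject counts as a failure in the PP run of the primary endpoint. Section 14.8 contains no sentence that keeps the subject there if follow-up then stops.

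**Possible size.** Let p be the true CCS rate in an arm and q the share of its failures removed. The remaining success rate is p / [1 − (1 − p)q]. The documents give no value for q; 10%, 25% and 50% are assumptions.

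- q = 10%: S+A 0.80/0.98 = 0.816; AA 0.60/0.96 = 0.625
- q = 25%: S+A 0.80/0.95 = 0.842; AA 0.60/0.90 = 0.667
- q = 50%: S+A 0.80/0.90 = 0.889; AA 0.60/0.80 = 0.750

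Difference, S+A minus AA, against the planned 0.20:

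| Failures removed | both arms | S+A only | AA only |
|---|---|---|---|
| 10% | 0.191 (−4%) | 0.216 (+8%) | 0.175 (−12.5%) |
| 25% | 0.175 (−12%) | 0.242 (+21%) | 0.133 (−33%) |
| 50% | 0.139 (−31%) | 0.289 (+44%) | 0.050 (−75%) |

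**With no true effect** (0.70 in both arms, starting from 116:58, one-sided 0.04, no continuity correction), equal removal leaves the rejection rate at 0.04. Removing 25% of S+A failures only raises it to 0.17; removing 25% of AA failures only lowers it to 0.005.

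**How plausible are these fractions?** At the original targets, expected failures are 134 × 0.20 + 67 × 0.40 = 53.6. Removing 10% means about 5 subjects. Removing 50% means about 27, which is the whole loss allowance in Section 10.6, every one of them a failure. The 50% row is an extreme.

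**The case against.** The strongest reply is that the harm is narrow. Section 10.4.3 tells sites to follow revised subjects for two years, and Sections 10.4.4, 10.4.6 and 10.4.7 do the same for cross-over, unblinded and injected subjects. A failure who stays to month 24 remains in the PP set, so 14.8 and 10.4.3 part only for one who leaves. Completion is a common PP criterion. The primary test uses mITT with a tipping-point analysis, plus multiple imputation above 10% missing, and no decision rule rests on the PP run. All of this stands and limits the weight of the point. It does not close the gap: Section 10.6 allows withdrawal for adverse events or at the investigator's discretion, and the missing-data analyses in 14.9 deal with unknown mITT outcomes, not with known failures left out of PP.

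Three stronger readings are tempting and are not supported.

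- A reader might infer that CCS failures as such are removed from the PP run. No section says so; early exit has to come with the failure.
- A reader might take the procedure in the exclusion clause to mean Subchondroplasty, so that exclusions fall on S+A and create a benefit. Sections 11.0 and 11.2 use study procedure for Subchondroplasty and/or arthroscopy, so an S+A-only reading is not established. Cross-over exists only for AA, and dropping those failures would work against S+A.
- A reader might infer that the clause lets poor responders be excluded. It speaks of actions, and a low KOOS score is an outcome. The clause is undefined and names no decision-maker, which is missing detail and not a licence to exclude on outcome.

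**Conclusion.** The point holds in a limited form. As written, the PP run of the primary endpoint drops a known CCS failure who leaves before month 24, and its month-12 comparison is conditioned on follow-up after month 12. The check can therefore be selected partly on outcome.

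Neither size nor direction can be read from the documents. Under assumed removal of 10% to 50% of failures in both arms, the planned 0.20 difference becomes 0.191 to 0.139. One-arm removal could raise or lower it. These figures rest on the plan's 0.80 and 0.60, on an unanchored removal fraction, and on removing failures only; loss unrelated to outcome would not bias the comparison in this way. At 10% removal the shift is small unless it falls on one arm. The mITT primary test and the sample size are untouched.

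**What to change.** In Section 14.8:

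1. Define the PP set separately for the month-12 and month-24 tests, requiring adherence and known CCS status only up to the tested visit.
2. State that a subject with an SSSI by that visit, or an observed KOOS pain failure at it, stays in the PP set as a failure regardless of later withdrawal. Reconcile this with 10.4.3.
3. List the remaining protocol-violation exclusions, and say what the clause on actions covers if it is kept. Decide them before database lock, blinded to arm and outcome. Section 17.3 describes the lock but no such step, and Section 7.0 reports that an interim analysis has already shown a high AA success rate.

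Adherence criteria up to the tested visit can stay; dropping them altogether would be a preference and is not needed here. The change is wording only and needs no new data. Its cost is a PP set that is larger and closer to mITT, so the two analyses will differ less.
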